9.4 Data collection and storage

Data will be handled in accordance with Sponsor protocols to ensure confidentiality and robust data management. Identifiable data will be collected by the research team in order to maintain contact with families to schedule follow-up visits, to allow linkage with the follow-up assessment data, and in order for Tower Hamlets Local Authority to identify the children and link the study data with NCMP data. All identifiable data will be stored separately from any clinical information, with a unique study identifier enabling the NCMP measurements to be added to the clinical data.

The identifiers will be retained for the length of the study as the child may need referring to a paediatric clinical service but will then be destroyed once Aim 2 of the study has been completed.

9.5 Follow-up procedures

Participants who have short stature for their age and parental heights will be identified using the screening algorithm at baseline. These participants will be referred for further clinical investigation. At follow-up, growth velocity will also be included in the screening algorithm, and any children found to have reduced growth velocity will be referred. Children will be followed up in a dedicated research clinic within Barts Health NHS Trust. [name] clinic is an established paediatric endocrine/growth clinic at the Royal London Hospital. Children will be seen and assessed as per standard clinical practice. They will have auxological assessment (height, weight, head circumference and recording of parental heights), a clinical review (history and physical examination). Patients requiring further investigations for short stature will follow a current best practice guideline investigation protocol. More detailed genetics (if a specific genetic disorder is suspected), Growth Hormone testing (as per standard departmental protocols) or referral to another speciality (e.g. gastroenterology) may be requested if clinically indicated.

9.6 Laboratory and radiological assessments

Laboratory and radiological investigations will not be performed as part of the study, but children who are identified in Aim 1 as having abnormal growth will be investigated in the referral clinic at the Royal London Hospital. This is not part of the study and represents normal clinical care.

9.7 Participant withdrawal

Participants will be able to withdraw from the study at any time and their data will be de-identified. Withdrawals from the study trigger completion of the exit form (Form 9).

9.8 End of Study Definition

The study will end for each child after their follow-up assessment is completed (after their school NCMP measurement at age 4-5 years). All fieldwork will be completed when the target sample of 630 children has been recruited (allowing for 5% loss to

follow up from the cohort of 630), with full measurements of all children on three occasions and developmental assessments on the subset of 150 children. Following the end of clinical assessments, the study will continue until the data have been analysed, linkage to NCMP measurements have been made, and those individuals identified with poor growth have been referred to [name] paediatric endocrinology clinic.

10. Statistical considerations

10.1. Sample size

The existing literature on growth screening shows that around 30-40% of children identified as having short stature will have an underlying medical disorder. During the course of this study, we estimate we will refer 12 out of 600 children for clinical investigation (based on referral of 2% children with the poorest growth). If the algorithm is successful at identifying children with a high likelihood of an underlying condition we would expect a total of 4 (35%) of the 12 children referred to be diagnosed with a medical condition. The sample size of 12 (2% of 600) gives us 85% power at 5% significance to detect a difference if the algorithm identifies less than 5% of children rather than the expected 35%. Therefore, if fewer than one (5% of 12) child referred to clinic is found to have an underlying medical condition we would be able to conclude that the algorithm had not achieved the goal of identifying children with a higher risk of underlying medical conditions.

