We estimate in this pilot study that 12 children will be referred for investigations (based on referral of 2% children with the poorest growth) and that 30-40% of these investigated in clinic will have an underlying medical disorder identified (n=4-5) based on the published literature. This pilot study is not designed to evaluate whether the age at diagnosis is significantly reduced using an automated screening approach; rather, our pilot data will inform feasibility and acceptability for a larger NIHR grant application to test the screening programme at scale with a primary outcome of age at diagnosis of medical disorders.
We will also investigate the inter-test agreement between the heights measured by caregivers using a smartphone app and heights measured by health professionals using a stadiometer.
Aim 2
Aim 2 of the pilot study will generate pilot data to investigate the best indicators to detect poor school readiness and/or developmental problems in early childhood.
We will investigate whether the addition of growth and development data to other environmental and socioeconomic variables increases the pick-up rate of children at risk of poor school readiness and/or children with delayed development.
Growth will be assessed using three height measurements as described above and development assessed as part of standard care by a Health Visitor and practice nurse.
As part of routine care, each child's development will be assessed using both the caregiver and health visitor components of the ASQ-3. Following the 2.0-2.5 year contact, a random sample of 150 children will also be invited to enrol in a sub-study to generate pilot data to investigate the correlation between the ASQ-3 and development assessed by a child psychologist using a

	Gold Standard development battery, the Griffiths Mental Development Scale (GMDS). The GMDS will be used to measure gross motor, fine motor, social, language, visual-spatial and practical reasoning skills. These data will inform a larger NIHR grant application to test the sensitivity of the parental and health visitor components of the ASQ-3.
	We will use the data to conduct analyses to test the hypothesis that linear growth failure either alone or in combination with additional factors identifies children with reduced neurodevelopment, who are therefore at risk of poor school attainment.
Study duration	3 years

5. Introduction

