At each of the 3 measurements of height we will identify the 2-3% of children with the poorest growth, as categorised by the algorithm (based on parental height, child height, and child growth velocity), in whom prior studies show a high prevalence (30-40%) of medical disorders. We will contact parents of these children to offer referral to the paediatric endocrinology clinic at the Royal London Hospital. A member of the study team will call the parents to inform them and will write to the child's GP to request a referral into the Royal London Hospital clinic via the e-referral system. We will evaluate acceptability and feasibility of the screening and referral process, using parental and primary care staff questionnaires. We will evaluate uptake by calculating the proportions screened, referred, investigated in clinic and diagnosed with medical disorders. At the clinic, children will be assessed by a paediatric endocrinologist and will undergo routine medical evaluation for short stature, with appropriate follow-up.

Development sub-study (age 2.0-2.5 years):

A random sample of 150 children will also be invited to enrol in a sub-study to generate pilot data on the sensitivity of the parent-reported ASQ-3 to assess child development compared to a gold standard development battery, the GMDS, undertaken by a psychologist. These children will undergo a neurodevelopmental assessment during their routine health visitor visit of their motor, cognitive, language and social skills using a standardized test battery (GMDS) by a child psychologist. Using data from the ASQ-3 developmental assessments conducted at baseline and follow up visits by the health visitor, we will investigate relationships between growth and development and assess content validity of the ASQ-3 by comparing it with the GMDS.

[figure not shown]
Qualitative sub-study (following the 2-2.5 year visit)

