10.2. Method of analysis

The overarching goal of this pilot study is to assess the feasibility of a growth screening programme. We are guided by Bowen's framework for feasibility studies, in which three key questions for feasibility are presented.¹⁸ These are: *Can it work? Does it work?* and *Will it work?* In this study we focus largely on the first question, can it work, and seek to provide some preliminary data on the second and third questions. Bowen's areas of focus for feasibility studies informs how we will answer these questions:

Can it work?

Acceptability: Focus groups with parents and health visitors will provide information on the acceptability of growth screening (see Qualitative Analyses, below). We will also examine ongoing study participation (retention rate).

Demand: The uptake of invitations to participate in the study (response rate), as well as uptake of the screening mobile phone app will provide data on demand for growth screening.

Integration: We will test integration into current health visiting systems by assessing the success of data linkage with NCMP, the proportion of parents who consent to NCMP data linkage, and through focus group interviews with health visitors.

Does it work? Will it work?

Below we outline how we seek to provide evidence for limited-efficacy testing, to gain an initial understanding of whether the growth screening algorithm is able to identify children for further clinical investigation. Acceptability, demand and integration are also interwoven into the data analysis strategy throughout.

Aim 1

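### Section 10.1 draws its failure criterion (0 of 12 diagnosed) from an 85% power statement, but at a 5% yield that criterion is met only 54% of the time

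*Protocol*

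**What the plan says.** Section 10.1 of the protocol starts from literature in which "around 30-40% of children identified as having short stature will have an underlying medical disorder". It takes 35% as the expected yield and sets the denominator: "we estimate we will refer 12 out of 600 children for clinical investigation". The power statement follows: "The sample size of 12 (2% of 600) gives us 85% power at 5% significance to detect a difference", the difference being "if the algorithm identifies less than 5% of children rather than the expected 35" per cent. No test, sidedness or critical value is named.

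The next sentence is presented as the consequence: "Therefore, if fewer than one (5% of 12) child referred to clinic is found to have an underlying medical condition", the algorithm may be judged to have missed its goal. The bracket in that sentence shows where the threshold comes from: 5% of 12 is 0.6, hence fewer than one.

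Section 10.2 puts the question of whether the algorithm works in second place. The study will mainly ask whether screening can work and "seek to provide some preliminary data on the second and third questions". The synopsis adds that "our pilot data will inform feasibility and acceptability for a larger NIHR grant application".

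**The concern.** The word *Therefore* makes the failure criterion look like the decision rule whose power is 85%. A criterion obtained by multiplying the poor yield by the sample size is an expected count, not the critical value of a test, and the two need not have the same operating characteristics.

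This is the protocol's only power calculation, and the criterion drawn from it is its only numerical one for the diagnostic yield among referred children. A reader would take it that an algorithm with a 5% yield would be caught with 85% probability. If one child in 12 were diagnosed, the same reader might conclude that the algorithm had passed an 85%-power check, when a 5% yield gives at least one diagnosis almost half the time.

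**Working it through.** **Inputs, all from section 10.1.** n = 12 children referred (2% of 600); poor yield 5%; expected yield 35%, within a literature range of 30-40%; significance 5%; stated power 85%; failure criterion fewer than 1, i.e. X = 0, where X is the number diagnosed. X is taken as Binomial(12, p).

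**Step 1: reproduce the 85%.** Test a null yield of 5% and reject for large X.

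- P(X = 0 | 5%) = 0.95^12 = 0.5404
- P(X = 1 | 5%) = 12 × 0.05 × 0.95^11 = 0.3413
- P(X = 2 | 5%) = 66 × 0.05² × 0.95^10 = 0.0988
- P(X ≥ 2 | 5%) = 1 − 0.5404 − 0.3413 = 0.118, above 5%
- P(X ≥ 3 | 5%) = 0.0196, below 5% (and below 2.5%)

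The critical value is therefore 3 of 12, one-sided or two-sided. Its power at 35% is 1 − (0.0057 + 0.0368 + 0.1088) = 0.8487, or 84.9%. The stated figure is reproduced.

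**Step 2: power of the written criterion.** P(X = 0 | p) = (1 − p)^12. At p = 5% this is 54.0%, so the criterion is not met 46.0% of the time. Setting (1 − p)^12 = 0.85 gives p = 1 − 0.85^(1/12) ≈ 1.3%. Because the text says less than 5%, lower yields are also relevant: 61.3% at 4%, 69.4% at 3% and 78.5% at 2%, all short of 85%.

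**Step 3: both rules side by side.**

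| True yield | 0 of 12 | 1 or 2 of 12 | 3 or more of 12 |
|---|---|---|---|
| 5% | 54.0% | 44.0% | 2.0% |
| 30% | 1.4% | 23.9% | 74.7% |
| 35% | 0.6% | 14.6% | 84.9% |
| 40% | 0.2% | 8.1% | 91.7% |

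The 0-of-12 criterion rarely condemns a good algorithm. Its weakness is in catching a poor one.

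**Step 4: can another test give 0 of 12 a power of 85%?** Take 35% as the null and reject for small X. The exact one-sided 5% test rejects at 0 or 1 of 12 (alpha 4.2%) and has 88.2% power at 5%; that is not the written rule. The exact two-sided version rejects in the lower tail only at 0 and has 54.0% power at 5%. No choice of test changes the probability in Step 2.

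**Step 5: dependence on n.** With the rule kept at zero diagnoses, 0.95^n is 59.9% for n = 10 and 39.7% for n = 18 (3% of 600). The number matters because the school-entry part of section 9.4 (Schedule of study interventions) says "At each of the 3 measurements of height we will identify the 2-3% of children with the poorest growth", so the total assessed may not be 12.

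**The case against.** The strongest reply is that neither sentence is wrong alone. The 85% is reproducible, and 0 of 12 does reject a 35% yield (one-sided p = 0.0057). The text gives only a sufficient condition for declaring failure; it does not say that 1 or 2 diagnoses means success, nor that 85% is the chance of seeing 0 of 12. On this view the fault is one connecting word. It is true that the link is implied, but the connective states a derivation that does not exist, and the reader is given no other rule to which the 85% could apply.

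Secondly, the 3-or-more rule is inferred. A continuity-corrected normal approximation also comes near 85% (87.0% one-sided, 83.7% two-sided), so the authors may have reached their figure another way. That stands, but it does not affect the 54%.

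Thirdly, the wording is aimed at detecting failure, and a rule of 0 or 1 of 12 would do that with 88% power at one-sided alpha 4.2% against 35%. Under that test, 1 of 12 would count as failure rather than as inconclusive. This is a legitimate alternative, although against 30%, the lower end of the expected range, its error rate is 8.5%.

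Finally, little hangs on the criterion. The primary endpoint is feasibility and acceptability, no stop/go decision is tied to 0 of 12, and sensitivity and specificity are to be studied in about 200 children with confirmed growth disorders, with controls. This limits the consequence but does not correct the statement.

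**Conclusion.** The point holds. The failure criterion in section 10.1 has 54% power at a 5% yield, not 85%, and reaches 85% only at a yield of about 1.3%. The 85% belongs to a rule the protocol does not state, most plausibly 3 or more of 12. What is wrong is the power attached to the criterion, not the inference drawn once 0 of 12 has been observed.

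The figures assume 12 children assessed, independent outcomes and a common yield; given these, the 54% requires no choice of test. The correction is worth making because the power calculation is the only one in the protocol and the pilot is meant to inform a larger application. It does not touch the primary endpoint.

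**What to change.** In section 10.1:

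- Pair the 85% with its critical value: with 3 or more of 12 diagnosed, conclude that the yield exceeds 5% (exact alpha 0.020, power 85% at 35%, 75% at 30%, 92% at 40%).
- Remove the *Therefore*. Keep 0 of 12 as a separate failure criterion and state its own properties: met 54% of the time at a 5% yield and 0.6% at 35%.
- Say that 1 or 2 of 12 meets neither rule and is inconclusive. If the sponsor prefers 0 or 1 of 12 as the failure rule, state the test (null 35%, one-sided, alpha 4.2%) and its 88% power instead; only 2 of 12 is then undecided.
- State that the figures are for 12 children assessed and will be recomputed for the number actually assessed.

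The cost is two or three sentences, with no extra children or procedures. There are two downsides. The stated power of the failure criterion becomes less favourable, and an inconclusive zone becomes visible: with 0 of 12 kept as the failure rule, its probability is 44% at a 5% yield, 24% at 30%, 15% at 35% and 8% at 40%.

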6.3. Primary endpoint

• Feasibility and acceptability of the screening pilot.

We will assess feasibility using Bowen *et al.*'s '8 areas of focus':¹⁷ acceptability, demand, implementation, practicality, adaptation, integration, expansion and limitedefficacy testing. To achieve this, we will employ a mixed methods evaluation including qualitative data collection using focus groups with caregivers and health visitors as well as questionnaires distributed to all caregiver participants in the study and all health visitors involved in growth and development assessments. We will also collect quantitative data on: uptake of growth measurements; number of successful

growth and development measurements; number of referrals successfully completed (i.e. referred to child growth clinic with participant attending one clinic appointment); number of participants consenting to identification of their child's anthropometric data from NCMP; and uptake of the smartphone app.

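### Section 10.1 sets its 85% power, 35% yield and failure conclusion on 12 children referred, which silently assumes that all 12 are assessed in clinic

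*Protocol*

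**What the plan says.** Section 10.1 of the protocol fixes the number: "we estimate we will refer 12 out of 600 children for clinical investigation (based on referral of 2% children with the poorest growth"). It then states the expected result: "we would expect a total of 4 (35%) of the 12 children referred to be diagnosed with a medical condition". The power statement is "The sample size of 12 (2% of 600) gives us 85% power at 5% significance to detect a difference". The two yields that it compares are 5% and 35%. The conclusion of failure follows "if fewer than one (5% of 12) child referred to clinic is found to have an underlying medical condition". Since 5% of 12 is 0.6, this means zero diagnoses.

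Other parts of the protocol treat referral and attendance as separate steps:

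- Section 9.4, under the school entry measurement: "We will contact parents of these children to offer referral to the paediatric endocrinology clinic at the Royal London Hospital". The study team then asks the GP to make the referral.
- Section 6.3 lists, among the feasibility data, the "number of referrals successfully completed (i.e. referred to child growth clinic with participant attending one clinic appointment").
- Section 6.1, hypothesis 2, puts high uptake of referral forward as something to be tested.

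The 30-40% benchmark is attached to three different groups. The synopsis (section 4, Aim 1 statistics) says "30-40% of these investigated in clinic will have an underlying medical disorder identified". Section 10.1 gives it for children identified as short. Section 9.4, and another sentence of the synopsis, give it for the 2-3% with the poorest growth.

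**The concern.** A child who is flagged but never seen in clinic cannot contribute a diagnosis through this pathway. The calculation in section 10.1 goes straight from 2% of 600 flagged to 12 with a known outcome, with no allowance for families who decline or do not attend. The synopsis does allow for loss at the measurement visits (95% attendance), but no similar allowance is made for the clinic.

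Two things are at stake. The stated power rests on an unstated condition. And the only decision rule in the plan gives a verdict on the algorithm from a count of zero, however few children were assessed. Low uptake would call for changes to the referral pathway and low yield for changes to the cut-offs, so the larger study needs a rule that keeps them apart. The shifting group behind the 30-40% leaves it unclear which proportion is being compared with 35%.

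**Working it through.** **Inputs.** From section 10.1: n = 12, rates 5% and 35%, significance 5% (sidedness not stated), power 85%. From the synopsis: benchmark range 30-40%. Assumed: attendance a, since the protocol gives no figure. Also assumed: each referred child attends independently, attendance is unrelated to having a disorder, and a diagnosis requires assessment in clinic.

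**Step 1: reproduce the 85%.** Let X be the number of diagnoses among 12 assessed children.

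- 3 or more of 12: P(X ≥ 3 | 5%) = 0.0196 and P(X ≥ 3 | 35%) = 0.849. This matches 85%.
- 2 or more of 12 would have P(X ≥ 2 | 5%) = 0.118, so 3 is the smallest threshold that keeps to 5%.
- A continuity-corrected normal approximation comes close (0.870 one-sided, 0.837 two-sided).

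All of these take 12 observed outcomes.

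**Step 2: allow for attendance.** With a 35% yield among those assessed, each referred child is diagnosed with probability 0.35a. Then power = P(X ≥ 3) for a binomial(12, 0.35a), and P(zero) = (1 − 0.35a)^12.

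| Attendance a | Diagnosed / referred (0.35a) | P(X ≥ 3) | P(zero) |
|---|---|---|---|
| 100% | 35% | 85% | 0.65^12 = 0.6% |
| 90% | 31.5% | 78% | 0.685^12 = 1.1% |
| 80% | 28% | 70% | 0.72^12 = 1.9% |
| 70% | 24.5% | 59% | 0.755^12 = 3.4% |
| 60% | 21% | 48% | 0.79^12 = 5.9% |
| 50% | 17.5% | 35% | 0.825^12 = 9.9% |

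P(zero) passes 5% when a < (1 − 0.05^(1/12)) / 0.35 = 0.2209 / 0.35 = 63%. With a yield of 30% the limit is 0.2209 / 0.30 = 74%, and with 40% it is 0.2209 / 0.40 = 55%.

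**Step 3: power by number assessed.** For k assessed, use the smallest threshold with P(X ≥ r | 5%) ≤ 0.05:

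| k assessed | Threshold r | P(X ≥ r at 5%) | Power at 35% |
|---|---|---|---|
| 12 | 3 | 0.020 | 0.849 |
| 11 | 3 | 0.015 | 0.800 |
| 10 | 3 | 0.012 | 0.738 |
| 9 | 3 | 0.008 | 0.663 |
| 8 | 3 | 0.006 | 0.572 |
| 7 | 2 | 0.044 | 0.766 |
| 6 | 2 | 0.033 | 0.681 |

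The 48% and 35% in step 2 keep the threshold at 3. A threshold tied to the number assessed recovers part of the loss at 7 or fewer.

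**Step 4: when does zero contradict 35%?** Zero of k has probability 0.65^k: 0.65^6 = 0.075 and 0.65^7 = 0.049. The one-sided 95% upper limit, 1 − 0.05^(1/k), is 39.3% for zero of 6, 34.8% for zero of 7 and 22.1% for zero of 12. So at least 7 assessed are needed. For a 30% yield it is 9 (0.70^8 = 0.058, 0.70^9 = 0.040); for 40% it is 6 (0.60^5 = 0.078, 0.60^6 = 0.047).

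**The case against.** A reader might infer more than the protocol supports. Five points on the other side deserve weight.

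- *That missed appointments would be read as failure.* The written trigger is zero diagnoses, and at 80% attendance a 35% yield gives zero only 1.9% of the time. Could is right; would is not.
- *That poor uptake and a poor algorithm cannot be told apart.* Section 9.4 plans the proportions screened, referred, investigated and diagnosed, and section 10.2 the numbers referred, attending and diagnosed. A reader of the results could separate the two. What stands is that the rule in section 10.1 does not use those counts.
- *That changing the denominator cures it.* Zero of 12 referred and zero of those assessed are the same event with the same probability. The denominator alters the reported percentage, not the trigger, so the rule has to depend on the number assessed.
- *That the benchmark is for investigated children, or that non-attenders are classed as having no condition.* Only one sentence in the synopsis supports the former; section 10.1 is consistent with its own wording. No text states the latter, and detailed handling may lie in an analysis plan that is not at hand.
- *That the effect is fixed at n = 12.* The protocol also speaks of 2-3%. With 3% of 600 = 18 referred and 60% attendance, the chance of zero is 0.79^18 = 1.4%, not 5.9%.

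It is also fair that the primary endpoint is feasibility and acceptability, and that sensitivity and specificity are examined separately in about 200 diagnosed children with controls, where attendance at the referral clinic plays no part. This limits the consequence. It does not remove the unstated condition behind the 85%, nor the verdict that section 10.1 attaches to a bare zero.

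**Conclusion.** The point holds as a defect in what section 10.1 fixes, and it is cheap to correct. The larger effect is on power: 85% is conditional on 12 children assessed and becomes 70% at 80% attendance, 48% at 60% and 35% at 50%, with the threshold held at 3. At 80% attendance the range is 58% to 79% for yields of 30% to 40%. The effect on the failure conclusion is smaller: zero diagnoses from an algorithm with a 35% yield rises from 0.6% at full attendance to 1.9% at 80% and 9.9% at 50%.

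The sizes rest on assumed attendance, on attendance being unrelated to disease, and on 12 referrals. The finding that 85% requires 12 known outcomes rests on none of the attendance assumptions.

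Separately, the rule that reproduces 85% (3 or more of 12) is not the written rule. At a true 5% yield, zero of 12 occurs only 0.95^12 = 54% of the time, so the 85% does not describe the failure rule even with full attendance.

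**What to change.** Amend sections 10.1 and 10.2 as follows.

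1. State that the 85% is conditional on 12 children assessed in clinic, name the test and threshold, and give the power for fewer (step 3). For orientation, 12 assessed needs about 14 referred at 90% attendance, 15 at 80%, 20 at 60% and 24 at 50%.
2. Define algorithm yield as diagnosed / assessed, with an exact confidence interval. Show diagnosed / referred only as programme yield, using the counts already planned in sections 9.4 and 10.2, with children not assessed shown as outcome unknown.
3. Make the failure conclusion depend on the number assessed: zero diagnoses contradicts a 35% yield at one-sided 5% only with 7 or more assessed; with fewer, report the result as inconclusive.
4. State one group for the 30-40% benchmark and use it in the synopsis, section 9.4 and section 10.1.

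The cost is wording: attendance is already collected, so no new data are needed. The downside is that the yield may rest on fewer than 12 children with a wide interval, and that children who attend may differ from those who do not. Both should be stated with the result.
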